**Table 4 Probe Set that have previously identified immune cell mechanisms specifically related to neutrophil function**

Gene	Probe ID	Gene	Probe ID
ABL1	202123_s_at	KLK7	239381_at
ACTA1	203872_at	KLK8	1552319_a_at
ACTA2	200974_at	KLK8	206125_s_at
ACTA2	215787_at	KLK9	233687_s_at
ACTA2	243140_at	LIMK1	204356_at
ACTB	200801_x_at	LIMK1	204357_s_at
ACTB	213867_x_at	LIMK1	208372_s_at
ACTB	224594_x_at	LRG1	228648_at
ACTB	AFFX-HSAC07/X00351_3_at	LTB4R	210128_s_at
ACTB	AFFX-HSAC07/X00351_5_at	LTB4R	216388_s_at
ACTB	AFFX-HSAC07/X00351_M_at	LTB4R	236172_at
ACTC1	205132_at	LTF	202018_s_at
ACTG1	201550_x_at	LYZ	1555745_a_at
ACTG1	211970_x_at	LYZ	213975_s_at
ACTG1	211983_x_at	MAPK1	1552263_at
ACTG1	211995_x_at	MAPK1	1552264_a_at
ACTG1	212363_x_at	MAPK1	208351_s_at
ACTG1	212988_x_at	MAPK1	212271_at
ACTG1	213214_x_at	MAPK1	224620_at
ACTG1	221607_x_at	MAPK1	224621_at
ACTG1	224585_x_at	MAPK1	229847_at
ACTG2	202274_at	MAPK11	206040_s_at
ACTG2	241148_at	MAPK11	211499_s_at

Gene	Probe ID	Gene	Probe ID
ACTN1	208636_at	MAPK11	211500_at
ACTN1	208637_x_at	MAPK12	1556340_at
ACTN1	211160_x_at	MAPK12	1556341_s_at
ACTN1	237401_at	MAPK12	206106_at
ACTN2	203861_s_at	MAPK13	210058_at
ACTN2	203862_s_at	MAPK13	210059_s_at
ACTN2	203863_at	MAPK14	202530_at
ACTN2	203864_s_at	MAPK14	210449_x_at
ACTN3	206891_at	MAPK14	211087_x_at
ACTN4	200601_at	MAPK14	211561_x_at
ACTR2	1554390_s_at	MAPK3	212046_x_at
ACTR2	1558015_s_at	MAX	208403_x_at
ACTR2	200727_s_at	MAX	209331_s_at
ACTR2	200728_at	MAX	209332_s_at
ACTR2	200729_s_at	MAX	210734_x_at
ACTR2	234210_x_at	MAX	214108_at
ACTR2	234212_at	MIF	217871_s_at
ACTR3	200996_at	MPO	203948_s_at
ACTR3	213101_s_at	MPO	203949_at
ACTR3	213102_at	MSN	200600_at
ACTR3	228603_at	MSN	233749_at
ACTR3	239170_at	MXD1	206877_at
ACTR3B	1555487_a_at	MXD1	226275_at
ACTR3B	218868_at	MXD1	228846_at
ADAM17	205745_x_at	MYB	204798_at
ADAM17	205746_s_at	MYB	215152_at
ADAM17	213532_at	MYC	202431_s_at
ADAM17	237897_at	MYH1	205951_at
AKT1	207163_s_at	MYH10	212372_at
AKT2	1560689_s_at	MYH10	213067_at
AKT2	203808_at	MYH11	1568760_at
AKT2	203809_s_at	MYH11	201495_x_at
AKT2	211453_s_at	MYH11	201496_x_at
AKT2	225471_s_at	MYH11	201497_x_at
AKT2	226156_at	MYH11	207961_x_at
AKT2	236664_at	MYH11	228133_s_at
AKT3	212607_at	MYH11	228134_at
AKT3	212609_s_at	MYH11	239307_at
AKT3	219393_s_at	MYH13	208208_at
AKT3	222880_at	MYH14	217545_at
AKT3	224229_s_at	MYH14	217660_at
AKT3	242876_at	MYH14	219946_x_at
AKT3	242879_x_at	MYH14	226988_s_at
ANPEP	202888_s_at	MYH14	232977_x_at
ANPEP	234458_at	MYH14	234290_x_at
ANPEP	234576_at	MYH15	215331_at
ARPC1A	200950_at	MYH16	1564072_at
ARPC1B	201954_at	MYH2	204631_at
ARPC2	207988_s_at	MYH3	205940_at
ARPC2	208679_s_at	MYH4	208148_at
ARPC2	213513_x_at	MYH6	214468_at
ARPC3	208736_at	MYH7	204737_s_at
ARPC4	211672_s_at	MYH7	216265_x_at
ARPC4	217817_at	MYH8	206717_at

Gene	Probe ID	Gene	Probe ID
ARPC4	217818_s_at	MYH8	34471_at
ARPC5	1555797_a_at	MYH9	211926_s_at
ARPC5	1569325_at	MYL1	209888_s_at
ARPC5	211963_s_at	MYL12A	1555976_s_at
ARPC5	237387_at	MYL12A	1555977_at
BDKRB1	207510_at	MYL12A	1555978_s_at
C5	205500_at	MYL12A	201318_s_at
C5AR1	220088_at	MYL12A	201319_at
CCL15	210390_s_at	MYL12B	221474_at
CCL2	216598_s_at	MYL2	209742_s_at
CCL20	205476_at	MYL3	205589_at
CCL3	205114_s_at	MYL4	210088_x_at
CCL5	1405_i_at	MYL4	210395_x_at
CCL5	1555759_a_at	MYL4	216054_x_at
CCL5	204655_at	MYL4	217274_x_at
CCL7	208075_s_at	MYL5	205145_s_at
CCR1	205098_at	MYL6	212082_s_at
CCR1	205099_s_at	MYL6	214002_at
CCR2	206978_at	MYL6B	204173_at
CCR2	207794_at	MYL7	219942_at
CCR3	208304_at	MYL9	201058_s_at
CCR5	206991_s_at	MYL9	244149_at
CD177	219669_at	MYLK	1563466_at
CD34	209543_s_at	MYLK	1568770_at
CEACAM1	206576_s_at	MYLK	1569956_at
CEACAM1	209498_at	MYLK	202555_s_at
CEACAM1	210610_at	MYLK	224823_at
CEACAM1	211883_x_at	MYLK2	231792_at
CEACAM1	211889_x_at	MYLK3	1562411_at
CEACAM3	208052_x_at	MYLK3	1568925_at
CEACAM3	210789_x_at	MYLK3	1568926_x_at
CEACAM3	217209_at	MYLK3	217623_at
CEBPA	204039_at	MYLK3	238834_at
CEBPE	214523_at	MYLPF	205163_at
CFL1	1555730_a_at	NCF1	204961_s_at
CFL1	200021_at	NCF1	214084_x_at
CFL1	230870_at	NCF2	209949_at
CFL1	236792_at	NCOA3	1562439_at
CFL2	224352_s_at	NCOA3	207700_s_at
CFL2	224663_s_at	NCOA3	209060_x_at
CFL2	233496_s_at	NCOA3	209061_at
CLEC4C	1552552_s_at	NCOA3	209062_x_at
CLEC4C	1555687_a_at	NCOA3	211352_s_at
CR1	206244_at	NFKB1	209239_at
CR1	208488_s_at	NFKB2	207535_s_at
CR1	217484_at	NFKB2	209636_at
CR1	217552_x_at	NFKB2	211524_at
CR1	244313_at	OSM	214637_at
CSF3	207442_at	OSM	230170_at
CSF3R	1553297_a_at	PAK1	1565772_at
CSF3R	203591_s_at	PAK1	209615_s_at
CXCL1	204470_at	PAK1	226507_at
CXCL2	1569203_at	PAK1	230100_x_at
CXCL2	209774_x_at	PDPK1	204524_at

Gene	Probe ID	Gene	Probe ID
CXCL2	230101_at	PDPK1	221244_s_at
CXCL3	207850_at	PDPK1	224986_s_at
CXCL5	207852_at	PDPK1	244629_s_at
CXCL5	214974_x_at	PDPK1	244630_at
CXCL5	215101_s_at	PDPK1	32029_at
CXCL8	202859_x_at	PECAM1	1558397_at
CXCL8	211506_s_at	PECAM1	1559921_at
CXCR1	207094_at	PECAM1	208981_at
CXCR2	207008_at	PECAM1	208982_at
CYBB	203922_s_at	PECAM1	208983_s_at
CYBB	203923_s_at	PGF	209652_s_at
CYBB	217431_x_at	PGF	215179_x_at
CYBB	233538_s_at	PIK3CG	206369_s_at
DEFB124	1568375_at	PIK3CG	206370_at
DEFB124	1568377_x_at	PIK3CG	239294_at
E2F1	2028_s_at	PIK3R5	220566_at
E2F1	204947_at	PIK3R5	227553_at
EGR1	201693_s_at	PIK3R5	227645_at
EGR1	201694_s_at	PIP5K1A	207391_s_at
EGR1	227404_s_at	PIP5K1A	210256_s_at
EGR3	206115_at	PIP5K1A	211205_x_at
ELANE	206871_at	PIP5K1B	205632_s_at
EZR	208621_s_at	PIP5K1B	217477_at
EZR	208622_s_at	PIP5K1C	212518_at
EZR	208623_s_at	PLCB2	204046_at
EZR	217230_at	PLCB2	210388_at
EZR	217234_s_at	PLD1	1557126_a_at
FES	205418_at	PLD1	177_at
FLT1	204406_at	PLD1	205203_at
FLT1	210287_s_at	PLD1	215723_s_at
FLT1	222033_s_at	PLD1	215724_at
FLT1	226497_s_at	PLD1	226636_at
FLT1	226498_at	PLD1	232530_at
FLT1	232809_s_at	PLPP6	227385_at
FOS	209189_at	PMAIP1	204285_s_at
FPR1	205118_at	PMAIP1	204286_s_at
FPR1	205119_s_at	PPP1CB	201407_s_at
FPR2	210772_at	PPP1CB	201408_at
FPR2	210773_s_at	PPP1CB	201409_s_at
GATA1	1555590_a_at	PPP1CB	228222_at
GATA1	210446_at	PPP1R12A	201602_s_at
GNAI1	209576_at	PPP1R12A	201603_at
GNAI1	227692_at	PPP1R12A	201604_s_at
GNAI2	201040_at	PREX1	224909_s_at
GNAI2	215996_at	PREX1	224925_at
GNAI2	217271_at	PRKCA	1560074_at
GNAI3	201179_s_at	PRKCA	206923_at
GNAI3	201180_s_at	PRKCA	213093_at
GNAI3	201181_at	PRKCA	215194_at
GNAO1	204762_s_at	PRKCA	215195_at
GNAO1	204763_s_at	PRKCB	207957_s_at
GNAO1	215912_at	PRKCB	209685_s_at
GNAO1	231951_at	PRKCB	227817_at
GNAZ	204993_at	PRKCB	227824_at

Gene	Probe ID	Gene	Probe ID
GNB1	200744_s_at	PRKCB	228795_at
GNB1	200745_s_at	PRKCB	230437_s_at
GNB1	200746_s_at	PRKCD	202545_at
GNB2	200852_x_at	PRKCE	206248_at
GNB3	206047_at	PRKCE	226101_at
GNB4	223487_x_at	PRKCE	234089_at
GNB4	223488_s_at	PRKCE	236459_at
GNB4	225710_at	PRKCE	239011_at
GNB5	1554346_at	PRKCG	206270_at
GNB5	204000_at	PRKCG	236195_x_at
GNB5	207124_s_at	PRKCH	206099_at
GNB5	211871_x_at	PRKCH	218764_at
GNB5	242404_at	PRKCH	230124_at
GNG10	201921_at	PRKCI	209677_at
GNG11	204115_at	PRKCI	209678_s_at
GNG11	239942_at	PRKCI	213518_at
GNG12	1555240_s_at	PRKCC	210038_at
GNG12	212294_at	PRKCC	210039_s_at
GNG12	222834_s_at	PRKCZ	1569748_at
GNG13	220806_x_at	PRKCZ	202178_at
GNG2	1555766_a_at	PRKD1	205880_at
GNG2	223943_s_at	PRKD1	217705_at
GNG2	224964_s_at	PRKD2	209282_at
GNG2	224965_at	PRKD2	241669_x_at
GNG3	222005_s_at	PRKD2	38269_at
GNG4	1555765_a_at	PRKD3	1554910_at
GNG4	1555867_at	PRKD3	211084_x_at
GNG4	1566513_a_at	PRKD3	218236_s_at
GNG4	205184_at	PRKD3	222565_s_at
GNG5	207157_s_at	PRKD3	242549_at
GNG7	206896_s_at	PRTN3	207341_at
GNG7	214227_at	PTAFR	206278_at
GNG7	228831_s_at	PTAFR	211661_x_at
GNG7	232043_at	PTAFR	227184_at
GNG8	233416_at	PTGS2	1554997_a_at
GNG8	234284_at	PTGS2	204748_at
GNGT1	207166_at	PTPRC	1552480_s_at
GNGT2	235139_at	PTPRC	1569830_at
H1F0	208886_at	PTPRC	207238_s_at
HSPA14	219212_at	PTPRC	212587_s_at
HSPA14	226887_at	PTPRC	212588_at
HSPA14	227650_at	PXN	201087_at
HSPA1L	210189_at	PXN	211823_s_at
HSPA1L	233694_at	RAC1	1567457_at
HSPA2	211538_s_at	RAC1	1567458_s_at
HSPA4	208814_at	RAC1	208640_at
HSPA4	208815_x_at	RAC1	208641_s_at
HSPA4	211015_s_at	RAC2	207419_s_at
HSPA4	211016_x_at	RAC2	213603_s_at
HSPA5	211936_at	RARA	1565358_at
HSPA5	230031_at	RARA	203749_s_at
HSPA6	117_at	RARA	203750_s_at
HSPA6	213418_at	RARA	211605_s_at
HSPA8	208687_x_at	RARA	216300_x_at

Gene	Probe ID	Gene	Probe ID
HSPA8	210338_s_at	REL	206035_at
HSPA8	221891_x_at	REL	206036_s_at
HSPA8	224187_x_at	REL	228812_at
HSPA9	200690_at	REL	235242_at
HSPA9	200691_s_at	REL	239486_at
HSPA9	200692_s_at	RELA	201783_s_at
HSPA9	232200_at	RELA	209878_s_at
ICAM1	202637_s_at	RELA	230202_at
ICAM1	202638_s_at	RELB	205205_at
ICAM1	215485_s_at	RXRA	202426_s_at
ICAM2	204683_at	RXRA	202449_s_at
ICAM2	213620_s_at	S100P	204351_at
IFITM1	201601_x_at	SELL	204563_at
IFITM1	214022_s_at	SOCS3	206359_at
IL1B	205067_at	SOCS3	206360_s_at
IL1B	39402_at	SOCS3	214105_at
IL1R1	202948_at	SOCS3	227697_at
IL1R1	215561_s_at	SPI1	205312_at
ITGAL	1554240_a_at	SPTBN1	200671_s_at
ITGAL	213475_s_at	SPTBN1	200672_x_at
ITGAM	205785_at	SPTBN1	212071_s_at
ITGAM	205786_s_at	SPTBN1	213914_s_at
ITGB2	1555349_a_at	SPTBN1	214856_at
ITGB2	202803_s_at	SPTBN1	215918_s_at
ITGB2	236988_x_at	SPTBN1	226342_at
ITPR1	1562373_at	SPTBN1	226765_at
ITPR1	203710_at	SPTBN1	228246_s_at
ITPR1	211323_s_at	SPTBN1	230540_at
ITPR1	216944_s_at	SPTBN1	242220_at
ITPR1	240052_at	SSH2	1554114_s_at
ITPR2	202660_at	SSH2	1555423_at
ITPR2	202661_at	SSH2	1555425_x_at
ITPR2	202662_s_at	SSH2	1560306_at
ITPR2	211360_s_at	SSH2	226080_at
ITPR3	201187_s_at	STAT3	208991_at
ITPR3	201188_s_at	STAT3	208992_s_at
ITPR3	201189_s_at	STAT3	225289_at
ITPR3	239542_at	STAT3	243213_at
JAK1	1552610_a_at	STAT5A	203010_at
JAK1	1552611_a_at	STAT5B	1555086_at
JAK1	201648_at	STAT5B	1555088_x_at
JAK1	239695_at	STAT5B	205026_at
JAK1	240613_at	STAT5B	212549_at
JAK2	1562031_at	STAT5B	212550_at
JAK2	205841_at	SYAP1	225154_at
JAK2	205842_s_at	TAC1	206552_s_at
JUN	201464_x_at	TACR1	208048_at
JUN	201465_s_at	TACR1	208049_s_at
JUN	201466_s_at	TACR1	210637_at
JUN	213281_at	TACR1	230908_at
KLK1	216699_s_at	TARP	211144_x_at
KLK10	209792_s_at	TARP	216920_s_at
KLK10	215808_at	TARP	217381_s_at
KLK11	205470_s_at	TBC1D22A	209650_s_at

Gene	Probe ID	Gene	Probe ID
KLK12	220782_x_at	TBC1D22A	210144_at
KLK12	233586_s_at	TBC1D22A	33778_at
KLK12	234316_x_at	TLN1	203254_s_at
KLK13	205783_at	TLN1	232763_at
KLK13	216670_at	TLN1	236132_at
KLK13	217315_s_at	TLN2	212701_at
KLK14	220573_at	TLN2	212703_at
KLK15	221462_x_at	TLN2	232625_at
KLK15	233477_at	TLR10	223750_s_at
KLK15	234495_at	TLR10	223751_x_at
KLK15	234966_at	TLR2	204924_at
KLK2	1555545_at	TLR4	1552798_a_at
KLK2	209854_s_at	TLR4	221060_s_at
KLK2	209855_s_at	TLR4	224341_x_at
KLK2	210339_s_at	TLR4	232068_s_at
KLK3	204582_s_at	TNF	1563357_at
KLK3	204583_x_at	TNF	207113_s_at
KLK3	231629_x_at	TNFRSF1A	207643_s_at
KLK4	1555697_at	TNFRSF1B	203508_at
KLK4	1555737_a_at	TREML2	219748_at
KLK4	224062_x_at	TTPAL	219633_at
KLK4	231782_s_at	TTPAL	228031_at
KLK4	233854_x_at	VAV1	206219_s_at
KLK5	222242_s_at	VCL	200930_s_at
KLK6	204733_at	VCL	200931_s_at
KLK7	205778_at	VPS37B	221704_s_at

### 13.7. Appendix 7: Reporting Standards for Missing Data

#### 13.7.1. Premature Withdrawals

Element	Reporting Detail
General	
 
• Subject study completion (i.e. as specified in the protocol) was defined as Subject whom have completed their final visit (day 84).
 
• Withdrawn subjects will not be replaced in the study.
 
• All available data from participants who were withdrawn from the study will be listed and all available planned data will be included in summary tables and figures, unless otherwise specified.
 

#### 13.7.2. Handling of Missing Data

Element	Reporting Detail
General	
 
• Missing data occurs when any requested data is not provided, leading to blank fields on the collection instrument:                             
 
○ These data will be indicated by the use of a “blank” in subject listing displays. Unless all data for a specific visit are missing in which case the data is excluded from the table.
 
○ Answers such as “Not applicable” and “Not evaluable” are not considered to be missing data and should be displayed as such.
 
 
 

Outliers	
 
• Any participants excluded from the summaries and/or statistical analyses will be documented along with the reason for exclusion in the clinical study report.
 

PD	
 
• Any values below the Lower Limit of Quantification (LLQ) will be assigned a value of ½ LLQ for display purposes in Figures and for computation of summary statistics. Any values above the Upper Limit of Quantification (ULQ) will be assigned to the ULQ for display purposes in Figures and for computation of summary statistics. Where biomarker concentrations are from an assay of an increased dilution factor the LLQ and ULQ will be multiplied by this factor. Note: Values sent to biostatistics are raw and have not taken into account dilution factor. LLQ and ULQ need to be taken into account prior to dilution factor and then imputed. Then Dilution factor needs to be applied. E.g. if raw value is 10 and dilution factor is 1:2 and ULD is 15, then this value is valid, but the final value should be 20.
 
• If the number of LLQ (and/or ULQ) values is large for an individual biomarker then an alternative analysis method, such as TOBIT analysis, may be required. “Large” is hard to define prospectively and may depend upon the dataset in question. Any such methodology will be documented in the statistical contributions to the study report.
 
• Imputed values will be used in tables and figures, unless the proportion of imputed values at a given time point is large, in which case the summary statistics may not be presented for that time point and/or alternative actions will be taken and documented in the study report.
 
• Where values are imputed, the number of such imputations will be included as a summary statistic in the relevant summary tables.
 

HRCT	
 
• No missing data imputation methods will be used.
 
• Note that for the HRCT data, there may be instances such that measurements from a particular Lobe cannot be distinguished between another Lobe, for example the iVlobe may be measured from both the LLL and LUL lobes. In such a case, the Lobe will be denoted as LLL + LUL. Therefore, for the statistical analysis purpose, since analysis is
 

Element	Reporting Detail																																									
	
performed on a lobar level, the LLL and LUL Lobes will be set to missing and will therefore not be included in the analysis. Below is a table of all possible scenarios, where the data is set to missing and not used in the statistical analysis:
 
  
 Lobes	Label	
 
 RUL	RML	RLL	LUL	LLL	
   
 x	x				RUL + RML	
 
 	x	x			RML + RLL	
 
 x		x			RUL + RLL	
 
 x	x	x			RUL + RML + RLL	
 
 			x	x	LUL + LLL	
  
	Lobes					Label	RUL	RML	RLL	LUL	LLL	x	x				RUL + RML		x	x			RML + RLL	x		x			RUL + RLL	x	x	x			RUL + RML + RLL				x	x	LUL + LLL
Lobes					Label																																					
RUL	RML	RLL	LUL	LLL																																						
x	x				RUL + RML																																					
	x	x			RML + RLL																																					
x		x			RUL + RLL																																					
x	x	x			RUL + RML + RLL																																					
			x	x	LUL + LLL																																					

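### SAP Section 13.7.2 scales the quantification limits by the dilution factor and also applies limits to raw values before dilution; used together, the two instructions count dilution twice

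*SAP*

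**What the plan says.** The rule is in the PD row of SAP Section 13.7.2 (amended RAP). It sets the imputations: "Any values below the Lower Limit of Quantification (LLQ) will be assigned a value of ½ LLQ for display purposes in Figures" and "Any values above the Upper Limit of Quantification (ULQ) will be assigned to the ULQ for display purposes in Figures"; both also feed the summary statistics. It then scales the limits: "Where biomarker concentrations are from an assay of an increased dilution factor the LLQ and ULQ will be multiplied by this factor".

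A Note follows at once. On the data it says: "Values sent to biostatistics are raw and have not taken into account dilution factor". On the order of steps it says: "LLQ and ULQ need to be taken into account prior to dilution factor and then imputed. Then Dilution factor needs to be applied". It closes with an example: "if raw value is 10 and dilution factor is 1:2 and ULD is 15, then this value is valid", with 20 as the final value. ULD is defined neither in the paragraph nor in the abbreviation list of Appendix 9; ULQ is evidently meant.

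The earlier RAP bound into the same file has the scaling sentence but not the Note. That is only background: the defect lies in the current text, where the two stand side by side.

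The evident users of the rule are sputum IL-6, IL-8 and TNFα (Sections 7.2.1 and 13.6.5), displayed in Tables 6.12 to 6.15.

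**The concern.** Limits and values have to be on the same scale. Limits multiplied by the dilution factor belong with dilution-corrected values; unmultiplied limits belong with raw values. The section prescribes scaled limits, says the data are raw, and says to multiply by the factor at the end. It does not say which scale the scaled limits are for, or that the Note takes precedence. A programmer who carries out every sentence compares raw values with scaled limits, imputes from scaled limits, and then multiplies again.

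More than the imputed values is at stake. The same section uses the frequency of imputation three ways: as a reported statistic, as grounds for withholding summary statistics at a time point, and as a trigger for an alternative such as Tobit analysis. Misclassifying values against the limits disturbs all three.

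**Working it through.** **Inputs**
- From Section 13.7.2: impute LLQ/2 below the lower limit and ULQ above the upper limit.
- From its example: raw 10, dilution 1:2 (taken as d = 2), upper limit 15, final value 20.
- Assumptions, because the SAP gives none: LLQ = 1, and d = 4 and d = 10 to show a range.

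**Three readings**, with raw value r, lower limit L, upper limit U and dilution factor d:
- A, the Note alone: compare r with L and U, impute L/2 or U, then multiply by d.
- B, the scaling sentence alone on corrected values: compare d·r with d·L and d·U, impute d·L/2 or d·U.
- C, both sentences on raw values: compare r with d·L and d·U, impute d·L/2 or d·U, then multiply by d.

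**Step 1. Reproduce the plan's example.**
- A: 10 is below 15, and 10 × 2 = 20.
- B: 20 is below 2 × 15 = 30, so 20.
- C: 10 is below 30, and 10 × 2 = 20.

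All three give the stated 20. The example excludes only the comparison of 20 with an unscaled 15, which would return 15.

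**Step 2. A and B agree everywhere.** r < L holds exactly when d·r < d·L, and likewise at the top. The imputed values also match: d·(L/2) = (d·L)/2 below, and d·U above.

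**Step 3. C against A** (taking d·L no larger than U, as in the illustrations):
- r < L: C gives d·(d·L/2) = d²·L/2; A gives d·L/2. Ratio d.
- r from L up to d·L: C imputes a quantifiable value and gives d²·L/2; A gives d·r. Ratio d·L/(2r), which runs from d/2 at r = L down to 1/2 as r nears d·L.
- r from d·L to U: no difference.
- r between U and d·U: C accepts the value and gives d·r; A caps it at d·U. Ratio r/U, between 1 and d.
- r > d·U: C gives d²·U; A gives d·U. Ratio d.

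**Step 4. Numbers**, with U = 15 and assumed L = 1:

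| d | raw r | A or B | C |
|---|---|---|---|
| 2 | 0.5 | 1 | 2 |
| 2 | 1.5 | 3 | 2 |
| 2 | 20 | 30 | 40 |
| 2 | 25 | 30 | 50 |
| 2 | 40 | 30 | 60 |
| 4 | 0.5 | 2 | 8 |
| 4 | 1.5 | 6 | 8 |
| 4 | 3 | 12 | 8 |
| 4 | 20 | 60 | 80 |
| 10 | 0.5 | 5 | 50 |
| 10 | 1.5 | 15 | 50 |
| 10 | 20 | 150 | 200 |

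At d = 2 the ratio in the second band lies between 1/2 and 1, so values there are lowered or unchanged, never raised. At larger d they can move either way: at d = 4, raw 1.5 goes up and raw 3 goes down.

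**The case against.** The strongest reply is that the section already contains the right procedure. The Note comes after the scaling sentence, identifies the data as raw, and sets the order: limits first, then imputation, then the factor. Scaling the limits before the comparison does not fit that order. The example sets 10 against 15 and never mentions 30, and its point seems to be that a final 20 is acceptable although it exceeds 15. The scaling sentence can be read as giving the limits on the final concentration scale, where it is also correct.

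Much of this stands. A reader might infer that the plan contains two incompatible procedures. It does not: Step 2 shows that each alone yields the same values. A careful analyst who lets the Note govern gets the right answer.

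What does not stand is the suggestion that the text settles the matter. No scale is attached to the scaled limits, no precedence is stated, and the example's value is valid against 15 and against 30 alike. It also never shows an imputed value, and the readings differ only for values that at least one of them imputes.

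**Conclusion.** The point holds as a drafting defect that permits a wrong calculation. It does not show that the calculation will be done wrongly. If both sentences are applied to raw data, values truly below LLQ come out d times too high, quantifiable values just above LLQ are imputed when they should not be, and values above ULQ are either accepted as measured or capped d times too high. Samples with d = 1 are unaffected.

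Two stronger inferences are tempting and unsupported. The first is that every imputed low value is d times too high. That is true only below LLQ; between LLQ and d·LLQ the error ratio runs from 1/2 to d/2. The second is that the error would hide a treatment effect, since Section 13.6.5 expects the cytokines to fall. The SAP does not say that values will reach LLQ, and it gives no LLQ, no share of values below it and no actual dilution factors; 1:2 appears only in the example. Neither the size nor the net direction of any bias can be stated.

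The reach is limited. Section 7.2 plans descriptive summaries for these exploratory markers and specifies no cytokine model. The primary mRNA analysis and the HRCT and lung-function analyses do not use this rule.

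**What to change.** In the PD row of Section 13.7.2:
- Delete the sentence that multiplies the limits, or restrict it expressly to values already corrected for dilution.
- Keep one order of steps: compare the raw value with the unscaled LLQ and ULQ; set values below LLQ to LLQ/2 and values above ULQ to ULQ; multiply once by the dilution factor.
- Correct ULD to ULQ.
- Replace the example with an out-of-range one that separates the readings: raw 25, ULQ 15, dilution 1:2, imputed 15, final 15 × 2 = 30. Counting dilution twice would give 50.

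The cost is one sentence deleted or qualified, one term corrected and one example replaced. No new data are needed, and programmers and QC are left with a single reading.

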**13.7.2.1. Handling of Missing and Partial Dates**

Element	Reporting Detail
General	
 
Partial dates will be displayed as captured in subject listing displays.
 

Adverse Events	
 
The eCRF allows for the possibility of partial dates (i.e., only month and year) to be recorded for AE start and end dates; that is, the day of the month may be missing. In such a case, the following conventions will be applied for calculating the time to onset and the duration of the event:                             
 
Missing Start Day: First of the month will be used unless this is before the start date of study treatment; in this case the study treatment start date will be used and hence the event is considered On-treatment as per Appendix 4: Study Phases and Treatment Emergent Adverse Events.
 
Missing Stop Day: Last day of the month will be used, unless this is after the stop date of study treatment; in this case the study treatment stop date will be used.
 
 
 
Completely missing start or end dates will remain missing, with no imputation applied. Consequently, time to onset and duration of such events will be missing.
 

Concomitant Medications/ Medical History	
 
Partial dates for any concomitant medications recorded in the CRF will be imputed using the following convention:                             
 
If the partial date is a start date, a '01' will be used for the day and 'Jan' will be used for the month
 
If the partial date is a stop date, a '28/29/30/31' will be used for the day (dependent on the month and year) and 'Dec' will be used for the month.
 
 
 
The recorded partial date will be displayed in listings.
 

